4.0 STUDY DESIGN

This is a prospective, single center, un-blinded, randomized controlled trial. Patients will be stratified by type of malignancy, and blocking will be used to ensure balance between study groups. Patients will be randomized to either Early Metabolic Resuscitation with Standard of Care (SC + EMR) or Standard of Care alone (SC).

Patients will be recruited from the Intensive Care Unit at The University of Texas MD Anderson Cancer Center with the intention of assessing the impact of (SC + EMR) on mortality: i) 28-day ii) during hospitalization, iii) in the ICU, and iv) at 90 days along with other known complications of septic shock relative to SC.

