- Hyperphosphatemia: Serum Phosphorous > 6.5 mg/dL (Note: Once phosphorus is below 6.5 mg/dL within 12 hours after meeting inclusion criteria, the patient can then be considered for the study. This is only a temporary restriction.)
- Patient with a history of metabolic abnormality in any one of the following amino acids: Alanine, Arginine, Cysteine hydrochloride, Glycine, Histidine, Isoleucine, Leucine, Lysine acetate, Methionine, Phenylalanine, Phosphoric acid, Proline, Serine, Threonine, Tryptophan, and Valine

Any other condition in which the ICU clinical team feels the patient should not be a candidate for the protocol.

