5.3 Study Enrollment Procedures

- A. Upon admission to the Emergency room or MICU, patients diagnosed with septic shock will be referred by the ICU attending to the designated study personnel who will then screen the patient for inclusion and exclusion criteria. The Basic Metabolic Panel (BMP) and patient medical chart history will be reviewed. If patient meets inclusion criteria (and no exclusion criteria) the patient's primary attending will be contacted for permission to enroll patient into the study. If the attending physician agrees, the patient (or if patient unable to consent, the patient's Legal Representative Power of Attorney or Next of Kin) will be approached.
- B. A discussion will be held with the next of kin and/or patient as appropriate to discuss the study procedures, possible adverse effects and research rationale. Informed consent will be mandatory and we will provide ample time to answer any questions or concerns about the protocol. A fully informed consent will be recorded in writing as per local guidance. It will be made clear to the participant and relatives that they are under no obligation to participate in the study and are free to withdraw

at any time, without giving a reason. Please see appendix for consenting material. If there is a possibility of pregnancy (defined as women <60 who have not been postmenopausal for at least one year or have not had a hysterectomy) then a serum or urine B-HCG test will be taken (with consent) prior to enrollment into the study. Refusal of pregnancy test will be considered grounds for exclusion.

The research coordinator will track all the potential candidates (patients meeting inclusion criteria) not included in the study in parallel due to logistical limitations (e.g. lack of research staff on weekends).

- C. Screening will be within 12 hours of patient being admitted to the ICU. Recruitment and initiation of study solution (where applicable) must occur both within twelve hours of the recorded onset of septic shock and admission to the MICU.

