8.0 SAFETY ASSESSMENTS

8.1 Theoretical and potential adverse events

The study intervention is assessing an infusion containing products, which are normal components of the diet and are not toxic in themselves. Although this trial is expected to be very safe there are four main etiologies by which harm may occur in any of the groups:

- 1. Fluid overload**
- 2. Electrolyte disturbances**
- 3. Hyper/hypoglycemia**
- 4. Hypersensitivity reactions**

Such events are frequent in an ICU, and medical personnel are well trained and experienced to deal with these situations. This, combined with the very close monitoring provided by ICU means that a serious adverse reaction is thought to be exceedingly unlikely. All of the described scenarios already have ICU management protocols.

As the study is unblinded, attending physicians and care team members will be aware of the contents of the solutions being infused. Thus, if the study team is not available to advise, the care team should be able to make a decision based on clinical factors and may use their discretion to discontinue the intervention where necessary.

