10.2 Sample Size Justification and Randomization

The rate of 28 day mortality from septic shock at the UT MD Anderson Cancer Center was 70% in 2017. With the objective of decreasing this rate to 40%, a sample size of 112 patients (56 per group) provides 90% power to detect a 30% absolute reduction in the rate of 28 day mortality using a two-sided chi-square test at the 0.05 significance level. We plan to use stratified randomization in a 1:1 fashion to assign patients into two groups, and a fixed block size consisting of 4 patients will be applied for this purpose. The randomization will be conducted in CORe (Figure 2).

Tables 3 displays effect sizes that correspond with conducting a test of equal proportions after randomizing 56 patients to each study arm. The first scenario in Table 3 is what we have currently provided in the protocol. Subsequent scenarios in Table 3 illustrate the change the in the effect size as the Type I error increases. Table 4 is provided to illustrate effect size results if the power is reduced to 80%. Smaller effect sizes are detectable if you increase Type I error or reduce power.

Table 3. Effect size with varying Type I error with Sample Size and Power controlled at 56 patients per study arm and 90%, respectively

Sample Size Per Study Group	Effect Size (percentage point change from $\hat{\pi}_0 = 70\%$)	Type I error
N = 56	-30% (0.70 vs 0.40)	0.05
N = 56	-27% (0.70 vs 0.43)	0.10
N = 56	-25% (0.70 vs 0.45)	0.15
N = 56	-24% (0.70 vs 0.46)	0.20

[figure not shown]
Estimates provided by (nQuery Advisor v7.0) for the difference between two proportions using a two-sided chi-square test.

Table 4. Effect size with varying Type I error with Sample Size and Power controlled at 56 patients per study arm and 80%, respectively

Sample Size Per Study Group	Effect Size (percentage point change from $\hat{\pi}_0 = 70\%$)	Type I error
N = 56	-26% (0.70 vs 0.44)	0.05
N = 56	-23% (0.70 vs 0.47)	0.10
N = 56	-21% (0.70 vs 0.49)	0.15
N = 56	-20% (0.70 vs 0.50)	0.20

Estimates provided by (nQuery Advisor v7.0) for the difference between two proportions using a two-sided chi-square test

Figure 2. Sample size and randomization

[figure not shown]

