The septic shock patients will be stratified by type of malignancy given that hematologic patients may be more morbid than solid tumor patients. SC + EMR: Early Metabolic Resuscitation plus Standard of Care SC: Standard of Care. Blue boxes represent the group of patients that will receive EMR plus Standard of Care intervention and the pink boxes represent the group that will receive Standard of Care alone.

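### A printed, fixed block size of 4 in an un-blinded single-centre trial would let anyone tracking a stratum deduce about one allocation in three before enrolment

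*Combined protocol and SAP*

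**What the plan says.** All references are to the combined protocol and SAP.

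- **Allocation.** Section 10.2 fixes the block length for its 1:1 stratified scheme: "a fixed block size consisting of 4 patients will be applied for this purpose". The Sample Size Justification row of the Summary Table prints the same fixed size, so it appears twice.
- **Strata.** Section 10.2, in the text under Figure 2: "The septic shock patients will be stratified by type of malignancy given that hematologic patients may be more morbid than solid tumor patients". Type of malignancy is normally known before a patient is enrolled.
- **System.** Section 10.2: "The randomization will be conducted in CORe". No other concealment measure is described.
- **Visibility.** Section 4.0: "This is a prospective, single center, un-blinded, randomized controlled trial". Section 8.1: "As the study is unblinded, attending physicians and care team members will be aware of the contents of the solutions being infused".
- **Discretion before enrolment.** Section 5.3: "the patient's primary attending will be contacted for permission to enroll patient into the study". Section 5.2 closes its list of exclusions with "Any other condition in which the ICU clinical team feels the patient should not be a candidate for the protocol".

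**The concern.** Central randomisation hides the list. It does not hide what can be worked out from earlier open allocations once the block size is known. In a 1:1 block of 4 the last place is always determined, and the third is determined whenever the first two match. Someone who knows the next arm and has a say in whether this patient enters can, deliberately or not, steer sicker or fitter patients towards one arm.

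The primary endpoint, 28-day mortality, is objective, so the exposure lies in who is enrolled and not in how the outcome is judged. Section 10.5 plans an unadjusted chi-square or Fisher's exact test for it, which gives no protection against an imbalance created at entry.

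**Working it through.** **The plan's own figure.** The documents give no figure for predictability. The one in the same section, 56 per group for 90% power, reproduces. With mortality 0.70 and 0.40 (mean 0.55) and two-sided alpha 0.05:

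n = [1.960 × √(2 × 0.55 × 0.45) + 1.282 × √(0.70 × 0.30 + 0.40 × 0.60)]² / 0.30² = 55.7, rounded up to 56 per group; power at 56 is 90.2%.

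The point below does not affect it.

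**Inputs for predictability.** Block size 4, fixed; 1:1, so two places per arm (Section 10.2); past allocations visible (Sections 4.0 and 8.1). Assumption: an observer logs allocations in order within each stratum.

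**Fixed blocks of 4.** Six orders are equally likely.

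| Place in block | Probability that the arm is certain | Probability that the best guess is right |
|---|---|---|
| 1 | 0 | 1/2 |
| 2 | 0 | 2/3 |
| 3 | 1/3 (first two match: 2 of 6 orders) | 1/3 × 1 + 2/3 × 1/2 = 2/3 |
| 4 | 1 | 1 |
| Sum | 4/3 | 17/6 |

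- Certain: (4/3) / 4 = 33.3%, or 112 × 1/3 = 37.3 patients if every block is complete.
- Best guess right: (17/6) / 4 = 17/24 = 70.8%, against 50% without tracking.
- Incomplete last blocks lower the certain share slightly: to no less than 36.0 patients (32.1%) with two strata, and no less than 31.5% in the three-stratum splits tried.

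**Alternatives.** Fixed 6 and 8 are by enumeration. The varying sizes are by simulation, with 56 patients per stratum and an observer who tracks the stratum and knows the set of sizes. The sizes are illustrative.

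| Blocks | Certain | Best guess right |
|---|---|---|
| Fixed 4 | 33.3% | 70.8% |
| Fixed 6 | 25.0% | 68.3% |
| Fixed 8 | 20.0% | 66.6% |
| Random 4/6 | 5.5% | 69.0% |
| Random 4/6/8 | 2.1% | 67.7% |

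An observer who knows nothing of the sizes and simply guesses the arm that is behind does about as well: 70.8% with fixed 4, and about 68% with random 4/6/8. The excess over chance falls from 20.8 to about 17.7 points, a relative drop of 3.1 / 20.8 = 15%.

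**What a bias could look like (assumption only).** Suppose selection acts only on the certain third, and there the mortality risk of enrolled patients differs by d points according to the predicted arm. The bias in the mortality difference is d/3. Under no true effect with 70% mortality, the standard error is √(2 × 0.70 × 0.30 / 56) = 0.0866.

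| Assumed d | Bias | Two-sided type I error (nominal 5%) |
|---|---|---|
| 5 points | 1.7 points | about 5.4% |
| 10 points | 3.3 points | about 6.7% |
| 20 points | 6.7 points | about 12% |

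No value of d comes from the documents.

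**The case against.** Several objections have force.

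- **Nobody is shown to be tracking.** A reader might infer that the ICU team will know one allocation in three. The documents do not support that. Section 8.1 says that staff know what is being infused; it does not say that anyone keeps the sequence by stratum. One in three is what a person who did so could deduce.
- **The roles are divided.** Under Section 5.3 the ICU attending refers, study personnel screen, the primary attending permits, and the patient or a representative consents. A primary attending may have seen no earlier allocation, and permission is not the last step. This reduces the exposure but does not remove it: the open-ended exclusion belongs to the ICU team, and under Section 10.4 the research coordinator and principal investigator handle every patient's data.
- **The strata are partly inferred.** Figure 2 is not shown. The cohort in Section 2.2 has 154 hematologic and 108 solid-tumour patients, 262 of 305, and the text does not say how patients like the other 43 would be stratified. An extra stratum changes the share little.
- **The harm might be repairable.** A reader might infer that selection bias could never be corrected. That is too strong: Section 7.1 collects baseline SOFA, demographics and disease status, and Section 10.5 plans logistic regression on patient characteristics. Adjustment would cover measured factors only.
- **Varying the blocks does not stop guessing.** This stands. The gain is almost wholly in certainty, and hiding the sizes hardly hinders someone who follows the running imbalance.

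**Conclusion.** The point holds as a conditional and avoidable design weakness that should be fixed. A fixed block of 4, printed in two places of an un-blinded single-centre protocol, makes an expected 33.3% of allocations deducible and 70.8% guessable for anyone who tracks a malignancy stratum, while entry depends partly on judgement. The percentages are exact for complete blocks and rest on the tracking assumption.

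A reader might go further and infer that enrolment is, or will be, biased by a known amount. The documents give no evidence of selective enrolment and no basis for its size; under the illustrative assumptions above the bias is 1.7 to 6.7 points, beside a planned effect of 30.

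**What to change.** 1. Have CORe generate each stratum with randomly varying block sizes, for example 4, 6 and 8.
2. Delete the block size from both the Summary Table and Section 10.2; changing only one leaves it disclosed. Suggested text: *Allocation is 1:1, stratified by type of malignancy, in permuted blocks of randomly varying size generated in CORe. Block sizes are kept in a restricted randomisation file, not available to staff who screen, enrol or treat patients.*
3. If recruitment has begun, apply the change to the allocations still to come.

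**Cost.** Two short text edits and a change to the randomisation set-up. The documents do not describe CORe's options, so its support for varying blocks needs confirming.

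The largest possible difference between arms within a stratum rises from 2 (fixed 4) to 4 (a block of 8 half filled with one arm). With two strata, both at the extreme in the same direction, the difference is 8. The interim look in Section 10.3, planned at 28 per arm, could then fall at 32 against 24, and the end of the trial at 60 against 52. The variance factor at the interim would rise from 2/28 = 0.0714 to 1/32 + 1/24 = 0.0729, about 2%; at the end it would rise from 2/56 = 0.0357 to 1/60 + 1/52 = 0.0359, about 0.5%. Fixed blocks of 4 do not guarantee exactly 28 per arm either, because each stratum can stop mid-block. The sample size of 112 is unchanged.

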10.3 Interim Analysis

The parameters indicated in the full analysis set comprised of 112 patient for detecting an effect size of -30% (.70 vs .40) with a 2-sided test and Type I error of 5% conferring > 90% power were used to develop interim stopping boundaries based on the method of Lan-DeMets with an O'Brien Flemming type spending function. An interim analysis will be conducted when the first 56 patients (28 patients randomized per treatment arm) have been evaluated for the primary endpoint. Figure 1 provides the stopping boundaries for early termination on a p-value scale for both superiority and futility (East Version 6.3.1). At the interim analysis, a p-value < 0.003 or a p-value > 0.864 elicits early stopping for superiority or futility, respectively. The PI will make the final determination whether to terminate or continue with the trial after evaluating the study results. Accrual will not be suspended while this analysis is being conducted.

Figure 1. Stopping boundaries (on a P-value scale) for early termination due to superiority or futility

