10.5 Data Analyses

Descriptive statistics including the mean, standard deviation, median, and range will be used to summarize continuous variables. Frequency counts and percentages will be used to summarize categorical variables. Categorical variables, including 28 day mortality, will be compared between intervention groups using a chi-square test, or Fisher's exact tests if more appropriate. Continuous variables will be compared between intervention groups using an independent samples t-test, or Wilcoxon rank-sum test if more appropriate.

Logistic regression will be used to assess relationships between patient characteristics and binary study outcomes of interest. Continuous variables, including the time on cardiovascular support and time on ventilator, will be compared using t-tests or Wilcoxon rank-sum tests.

Time to event analyses will be conducted using Cox proportional hazards regression. For 28-day mortality, living patients will be censored after one month after the treatment was given. For overall survival, patients will be followed until time of death or date of last follow-up (maximum 6 months). Kaplan-Meier plots will be used to visually compare time to death from any cause between intervention arms followed by a log-rank test to compare survival distributions.

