10.6 Safety monitoring for Patients assigned to (SC + EMR)

Patient safety will be monitored group sequentially for the first 50 patients in (SC + EMR) group. The monitoring rule will be applied in cohorts of size 10 during the 7 days of treatment.

Patient safety will be monitored to ensure that the rate of select AEs described in Section 8.2 (which include: severe fluid overload, untreatable electrolyte abnormalities, severe hyper/hypoglycemia, allergic reactions) does not exceed 25%. If the AE rate exceeds 25%, then the novel treatment approach of (SC + EMR) exceeds an acceptable rate and the trial will suspend accrual, while at the same time, protecting patients from the burden of being exposed to an untoward therapy.

We will employ Bayesian stopping boundaries derived using a beta-binomial distribution. We will consider the treatment as acceptable if the AE rate during the first seven days post administration of (SC + EMR) is below 25%. The following prior probability for the AE rate will be modeled with a beta distribution (1, 1). Allowing θ_T to denote the true rate of AEs, the trial will suspend accrual if the $\text{Prob}(\theta_T > 0.25 | \text{data}) > 0.80$. Patients will be monitored in cohorts of size 10 according to the following stopping boundaries displayed in Table 3.

Table 4 illustrates the operating characteristics associated with the Bayesian stopping rule. The probability of stopping accrual early is 61% if the true AE rate is 30%.

Table 3. Stopping Boundaries assuming prior $\theta_T \sim \text{beta}(1, 1)$

Number of Patients Evaluated	Recommended stopping accrual if \geq AEs are observed
10	4-10
20	7-20
30	10-30
40	13-40
50	15-50

*stopping boundaries and operating characteristics supplied using

<https://ibl.mdanderson.org/BTM/>

Table 4: Operating Characteristics for the Bayesian Sequential Design

True AE Rate	Probability of Stopping Accrual Early	Average Sample Size
0.1	0.014	49.5
0.2	0.180	43.7
0.3	0.610	29.9
0.4	0.928	17.7
0.5	0.996	12.3

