11.4.4 Monitoring

Protocol compliance will be assessed by review of records, including inpatient electronic records, by the research team during the collection of study outcomes. All consent documents and any other information collected non-electronically will be reviewed by the principle investigator. The MD Anderson Data and Safety Monitoring Board (DSMB) may decide to audit the research at any stage and review the progress of the research at the frequency they so desire.

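### The interim futility cut-off in 10.3 is a two-sided p-value with no sign, so it stops less often once EMR mortality exceeds SC mortality, and no mortality-harm criterion is stated

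*Combined protocol and SAP*

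**What the plan says.** Section 10.3 plans one interim analysis after the first 56 patients (28 per arm) have been evaluated for 28-day mortality. It uses Lan-DeMets boundaries of O'Brien-Fleming type, built "with a 2-sided test and Type I error of 5" per cent. The operative sentence is: "At the interim analysis, a p-value < 0.003 or a p-value > 0.864 elicits early stopping for superiority or futility, respectively". The caption of Figure 1 in that section reads "Stopping boundaries (on a P-value scale) for early termination due to superiority or futility". The figure itself cannot be seen in the available text.

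The test at the look is not named. Section 10.2 sizes the trial "using a two-sided chi-square test at the 0.05 significance level", while 10.5 says that categorical outcomes, 28-day mortality among them, "will be compared between intervention groups using a chi-square test, or Fisher's exact tests if more appropriate".

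On who acts, 10.3 says "The PI will make the final determination whether to terminate or continue with the trial after evaluating the study results". Section 11.4.4 says the DSMB "may decide to audit the research at any stage and review the progress of the research at the frequency they so desire", and 12.4 lets the IRB and government agencies discontinue the study. The other stopping rule, in 10.6, counts selected adverse events in the EMR arm: "severe fluid overload, untreatable electrolyte abnormalities, severe hyper/hypoglycemia, allergic reactions". Deaths are not among them.

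**The concern.** A two-sided p-value measures distance from equality and does not show which arm did worse. A futility rule should stop more often as the treatment effect moves from benefit to none to harm. A rule that fires on a large two-sided p-value fires most often at no difference and less often as harm grows, because harm makes the p-value small again. The only other cut-off, p < 0.003, can be met by excess EMR deaths, but the text labels that result superiority.

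This is the only planned interim comparison of mortality, in an unblinded trial whose primary endpoint is death. Accrual continues during the look, and the PI decides. If the stated rule is silent or misleading when EMR deaths are in excess, the decision rests on discretion alone.

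**Working it through.** **Inputs.** SC mortality 70%, design alternative 40%, 56 per arm, two-sided 0.05 (10.2); 28 per arm at the look, cut-offs 0.003 and 0.864 (10.3). EMR mortality of 50, 60, 80 and 90%, and SC mortality of 50 and 60%, are assumed scenarios.

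**Step 1: the scale of the cut-offs.** O'Brien-Fleming-type spending of 0.025 per side at half information gives z = 2.963, two-sided p = 0.00305. This reproduces the plan's 0.003 as a two-sided value. Read as one-sided, 0.003 would be z = 2.75, which is not the O'Brien-Fleming value. On the same two-sided scale, 0.864 is |z| = 0.171.

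**Step 2: where 0.864 may come from.** The futility spending settings are not stated, so this step rests on assumptions. The unpooled drift is 0.30/√(0.45/56) = 3.347, so fixed-design beta is 0.083. O'Brien-Fleming-type beta spending then spends 0.0142 at half information. The one-direction bound is 3.347 × √0.5 − 2.193 = +0.173, two-sided p = 0.862. Over 90 to 91.6% power, with pooled or unpooled variance, a one-direction bound gives p = 0.75 to 0.94 and a symmetric inner wedge gives 0.71 to 0.82. This suggests, without proving it, that the bound was Z ≤ +0.17 and lost its sign when written as a p-value.

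**Step 3: the rule as written.** With Z > 0 meaning fewer EMR deaths,

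Z = [(d_SC − d_EMR)/28] / √[2p̄(1 − p̄)/28], p̄ = (d_SC + d_EMR)/56.

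Over all 29 × 29 outcomes, the largest p-value with unequal deaths is 0.789 (for example 13 v 14). So p > 0.864 requires equal deaths.

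Example: 20 SC v 26 EMR deaths. p̄ = 46/56 = 0.821, difference −6/28 = −0.214, standard error 0.102, Z = −2.09, p = 0.036 (Fisher 0.078). Neither cut-off is met.

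**Step 4: stopping probabilities** (exact product binomial, SC 70%, in %).

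| EMR mortality | 40 | 50 | 60 | 70 | 80 | 90 |
|---|---|---|---|---|---|---|
| Futility as written, chi-square | 0.7 | 3.3 | 8.2 | 11.6 | 8.5 | 2.1 |
| Futility as written, Fisher | 2.5 | 10.2 | 24.3 | 33.8 | 25.2 | 7.0 |
| Signed, Z ≤ 0.17 | 1.4 | 7.9 | 25.8 | 55.8 | 84.8 | 98.3 |

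The unsigned p < 0.003 is also met through excess EMR deaths, in 1.4% of looks at EMR 80% and 11.6% at 90%. Counting both cut-offs, the written rule stops 11.9%, 9.9% and 13.8% of the time at EMR 70, 80 and 90%, so it continues 90.1% of the time at 80% and 86.2% at 90%. The chance of more EMR deaths with no cut-off met is 74.9% at EMR 80% and about 85% at 90%.

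**Step 5: sensitivity to the 70%.** At SC 50% and EMR 50/60/70%, futility stops are 10.6/8.0/3.3% as written and 55.3/81.4/95.4% signed. At SC 60% and EMR 60/70/80%, they are 10.8/8.2/2.9% (the last is 2.95% before rounding) and 55.4/82.4/96.5%. The pattern is the same.

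**Step 6: expected number of patients** if the rule is followed (56 at an interim stop, otherwise 112, before overrun). As written v signed: 106.5 v 64.5 at EMR 80%, and 104.3 v 56.9 at EMR 90%.

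**The case against.** The strongest reply is that the boundary lives in a figure that cannot be seen, and the numbers themselves point to a directional bound. On that view the percentages describe a rule nobody designed, and what remains is a clarification. It stands that a direction shown only in Figure 1 cannot be excluded; the finding covers the text and caption only. But the caption describes a p-value scale, and the sentence that states the rule has to be right on its own. If a directional bound was designed, the text states a different one.

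Second, nobody would apply an unsigned p-value blindly: the PI evaluates the results, the DSMB may review at any time, and the IRB may stop the study. That is fair, and the 90% and 86% apply only if the rule is followed literally. None of these bodies is given a mortality criterion, however, and 8.3 limits what is reported as serious in the EMR group to three scenarios, none of which is death.

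Third, p < 0.003 can be reached through harm. This is true and is counted above. "Stops less often" therefore describes the futility cut-off; total stopping at EMR 90% (13.8%) is slightly above that at no effect (11.9%).

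Fourth, a signed futility bound makes a formal finding of harm unlikely. This also stands, and it is a real trade-off, set out with the costs of the fix. Finally, the efficacy inference is barely touched, which is correct: the defect lies in how the trial behaves under no effect and harm.

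**Conclusion.** The concern holds. As worded, the futility rule in 10.3 fires only on equal deaths under the uncorrected chi-square test, and its chance of firing falls from 11.6% at no effect to 8.5% and 2.1% as EMR mortality rises to 80% and 90% with SC at 70%. A signed version of the same number would give 55.8%, 84.8% and 98.3%. The text gives no mortality-harm criterion, in 10.3 or elsewhere. Leaving the test unnamed adds a threefold uncertainty in stopping under no effect (11.6% with chi-square, 33.8% with Fisher).

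The stopping probabilities rest on 28 per arm, independent binomial outcomes and literal use of the rule; the direction of the result does not depend on the 70% assumption. What was intended remains uncertain, because the figure and the futility spending settings are not available. This should be corrected before the interim look.

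**What to change.** Amend 10.3 to state the boundaries on the signed Z scale of the uncorrected chi-square test used in 10.2, with Z > 0 meaning lower mortality on SC+EMR:

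- Superiority: Z ≥ 2.96.
- Futility, non-binding: Z ≤ 0.17. State in words that every result with higher EMR mortality falls here, including one with two-sided p < 0.003. This adds no separate harm bound.
- Check both values against the East output behind Figure 1, and report the stopping probabilities and power.

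As a secondary change, reconcile 10.3 with 11.4 so that the DSMB already named there reviews the interim comparison and makes its recommendation to the PI.

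**Cost.** An amendment and a re-run of the boundary properties; no added patients. Futility stopping rises from 11.6% to 55.8% under no effect, from 8.2% to 25.8% at EMR 60%, and from 3.3% to 7.9% at EMR 50%. Exact power, with a final critical value of 1.969, is as follows:

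| EMR mortality | No futility rule | As written | Signed |
|---|---|---|---|
| 40% | 89.6% | 89.4% | 89.3% |
| 50% | 57.7% | 57.4% | 57.2% |
| 60% | 20.1% | 19.9% | 19.8% |

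If the boundary is followed, the chance of a formal two-sided finding that EMR is worse falls from 23.0% to 0.1% at EMR 80%, and from 77.7% to 0.1% at EMR 90%. Because the boundary is non-binding, the trial may still continue where that finding is wanted.

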10.4 Data Monitoring

During the course of the study, safety and data quality monitoring will be performed on an ongoing basis by the Research Coordinator and the Principal Investigator. The clinical research coordinator will be responsible for collecting and recording all clinical data. This includes ensuring that all source documents exist for the data on the case report forms, ensuring all fields are completed appropriately, and all corrections are done according to Good Clinical Practice (GCP's). Any inconsistencies/deviations will be documented. The P.I. will review the obtained data for each patient on an ongoing basis.

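### The PI of this un-blinded trial evaluates the interim mortality comparison and makes the final stop-or-continue decision, while the existing DSMB has no stated role in it

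*Combined protocol and SAP*

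**What the plan says.** Section 4.0 describes the design: "This is a prospective, single center, un-blinded, randomized controlled trial".

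Section 10.3 sets the interim look: "An interim analysis will be conducted when the first 56 patients (28 patients randomized per treatment arm) have been evaluated for the primary endpoint". The limits "were used to develop interim stopping boundaries based on the method of Lan-DeMets" with an O'Brien-Fleming-type spending function, and at the interim "a p-value < 0.003 or a p-value > 0.864 elicits early stopping for superiority or futility, respectively". The decision rule follows: "The PI will make the final determination whether to terminate or continue with the trial after evaluating the study results". The section ends: "Accrual will not be suspended while this analysis is being conducted".

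Section 10.4 says that "safety and data quality monitoring will be performed on an ongoing basis by the Research Coordinator and the Principal Investigator", and that the PI looks at each patient's data as they accumulate.

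The DSMB appears only in section 11.4. Under 11.4.2 it oversees data integrity and receives adverse-event and annual reports, prepared with the trial statisticians' help. Under 11.4.3 the PI may pass protocol deviations to it. Under 11.4.4, "The MD Anderson Data and Safety Monitoring Board (DSMB) may decide to audit the research at any stage", and it may review progress as often as it chooses. Section 12.4 lists who may modify or discontinue the study: the IRB, OHRP, FDA and other government agencies. The DSMB is not on that list.

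**The concern.** An interim comparison is normally kept from those running a trial so that knowledge of the trend cannot affect later enrolment or care. Here the plan does the reverse: the PI evaluates the comparison and has the last word. Section 10.3 also does not limit who else in the unit may learn the result.

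Mortality is hard to misclassify, but it can still be affected by who enters the trial, how patients are managed and who is counted. The protocol leaves judgement in each of these:

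- **Entry.** Section 5.2 ends with an open-ended exclusion at the ICU team's discretion, and section 5.3 requires the attending's permission before a patient is approached. Section 10.2 uses fixed blocks of 4, so with open allocation some upcoming assignments can be guessed.
- **Treatment.** Sections 8.1 and 9.0 let clinicians discontinue the intervention on their own judgement.
- **Who is counted.** Section 6.4 removes from the study patients who reach Comfort Care status in the ICU. By contrast, it keeps following those who start renal replacement. It does not say whether the 28-day outcome of removed patients still counts.

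A known trend could influence any of these decisions, in an arm everyone can see.

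**Working it through.** **1. Who does what at the interim.**

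| Function | Assigned to | Section |
|---|---|---|
| Evaluates the interim comparison | PI | 10.3 |
| Final stop/continue decision | PI | 10.3 |
| Ongoing patient-level review | PI and research coordinator | 10.4 |
| Data integrity, adverse-event and annual reports | DSMB | 11.4.2 |
| Optional audit or progress review | DSMB | 11.4.4 |
| Independent receipt of, or recommendation on, the interim comparison | nobody named | – |

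**2. Superiority limit reproduced.** Inputs from 10.2 and 10.3: two-sided 5%, that is 0.025 per side, and information fraction t = 56/112 = 0.5. O'Brien-Fleming-type spending per side is 2[1 − Φ(z/√t)], with z = Φ⁻¹(1 − 0.0125) = 2.241. Then 2.241/√0.5 = 3.170 and 2[1 − Φ(3.170)] = 0.001525. Doubled, this gives p = 0.00305, which matches the stated 0.003.

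**3. Futility limit taken as given.** O'Brien-Fleming-type beta-spending variants gave two-sided p of about 0.75 to 0.81, not 0.864. The beta-spending details are not stated and the boundary figure is not shown, so this is not counted as an error. The point does not depend on it.

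**4. How often the trial continues.** All death counts (i, j) at 28 versus 28 were enumerated with binomial weights. The uncorrected chi-square p-value comes from z = [(i − j)/28] / √[p̄(1 − p̄)·2/28], with p̄ = (i + j)/56.

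| True mortality | P(p < 0.003) | P(p > 0.864) | Neither |
|---|---|---|---|
| 0.70 v 0.70 | 0.0026 | 0.1160 | 1 − 0.0026 − 0.1160 = 0.881 |
| 0.70 v 0.40 | 0.2253 | 0.0074 | 1 − 0.2253 − 0.0074 = 0.767 |

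With equal arms the futility limit is crossed only when the death counts tie. The largest p-value for a one-death difference is at 14 versus 13: p̄ = 27/56 = 0.482, SE = √(0.482 × 0.518 × 2/28) = 0.134, z = 0.0357/0.134 = 0.267, p = 0.789, which is below 0.864.

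**5. How many patients follow the look.** The look needs 28 days of follow-up on patient 56, and accrual does not pause, so the number is below 56. The documents give no accrual rate. Assuming, for illustration only, that 112 patients accrue evenly over 12 to 36 months, the 28-day window alone takes in 112 × 28/365 = 8.6 down to 112 × 28/1095 = 2.9 patients. That leaves about 47 to 53, less those who enter while the analysis is run.

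**The case against.** The strongest reply has three parts. The endpoint is death. Numeric limits are fixed in advance. And in an open-label, single-centre trial whose PI already reviews every patient's data, the PI can form a view of mortality by arm with or without a formal report. All three are true. The last means that rerouting the report reduces the PI's knowledge but does not remove it. None of them supplies an independent recipient for the comparison.

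A reader might also infer more than the documents support:

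- **That the PI decides alone.** Section 10.3 gives the PI the last word and names nobody else, but it does not say alone. The bodies in 12.4 can stop the study from outside.
- **That the DSMB is confined to annual reports and audits.** It also receives adverse-event reports, oversees data integrity and may review progress when it chooses. What is missing is an assigned role at the interim.
- **That the PI controls entry and Comfort Care decisions.** Section 5.3 spreads referral, screening and permission over several people, and no section gives Comfort Care decisions to the PI. The risk is that the result becomes known within the unit.
- **That the limits lose their error rates.** Continuing past the superiority limit does not inflate type I error, and the plan does not say whether the futility limit is binding. Claiming benefit short of p < 0.003 would inflate it. The text does not authorise that, though no independent check against it is described.
- **That a misleading trend is likely.** With 70% mortality in both arms, the exact chance of a gap of 10 points or more at 28 per arm is 46.5%, under one half. That measures sampling noise, not bias.
- **That continued accrual is itself a flaw.** It is not.
- **That section 10.6 has the same problem.** Its rule counts adverse events in the SC + EMR arm only, so an argument about comparative mortality does not carry over.

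**Conclusion.** The point stands as one of governance. Section 10.3 states a rule; it is not silent on the matter. The PI evaluates comparative mortality and decides, so the two limits are advisory, and no independent body is assigned to receive the comparison or recommend on it.

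The most probable outcome is continuation with the PI informed: about 88% under no effect and 77% under the planned effect. These figures assume 28 patients per arm, an uncorrected two-sided chi-square test, the stated limits, and 70% control mortality as in 10.2. They say how often the situation arises, not how much bias follows. The plan should be changed before the interim analysis, because knowledge of the comparison cannot be withdrawn afterwards.

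**What to change.** In section 10.3, state that:

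- the trial statistician prepares the by-arm interim report and sends it only to the MD Anderson DSMB;
- the DSMB applies the pre-stated limits and recommends stopping or continuing;
- the PI and the ICU team receive that recommendation and nothing by arm.

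In section 10.4, state that the PI's ongoing review covers individual patient data for quality and safety, and that no outcome summaries by arm are produced for the PI. Without this second change, the first is easily bypassed.

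The cost is protocol wording and one DSMB review. The board exists, and the trial statisticians already help report to it under 11.4.2. Sample size, stopping limits and treatment are unchanged.
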